14.2.7 Other Toxicities

For toxicities that do not fall into one of the scenarios above, management will be as follows:

Grade 1 and 2: Participants may continue HP at the discretion of the site investigator with careful follow-up.

Grade 3 and 4: Study drugs should be held until symptoms have resolved (or until \leq Grade 2 or within normal limits). Study drugs may be permanently discontinued at the discretion of site investigator.

Site investigators are strongly encouraged to discuss discontinuations and reintroductions of study treatment with the core investigators to ensure consistency across sites.

If study drugs are suspended for any reason, participants in Arm A will have 8 weeks from enrollment to complete 28 doses of HP. Participants in Arm B will have 16 weeks from enrollment to complete at least 11 doses of HP. If the break in treatment is longer than 4 weeks, the participant will need to be rescreened for TB before recommencing HP.

14.3 Pregnancy

Pregnancy is an exclusion criteria for enrollment. An individual who becomes pregnant during the study drug treatment phase will be managed according to the plan described in Section 12.

14.4 Criteria for Discontinuation of Study Medications

14.4.1 Criteria for Permanent Discontinuation

- Discontinuation for an Individual Participant
- Drug-related toxicity requiring tx discontinuation
- Pregnancy or breastfeeding. HP will be discontinued and the participant will be referred to routine care.
- Diagnosed with active TB disease
- Completion of study events
- Request by participant to terminate treatment
- Clinical reasons believed life threatening by the physician, even if not addressed in the toxicity section of the protocol
- Acquires HIV infection while on study

14.4.2 Premature study discontinuation

- Request by the participant to withdraw
- Pregnancy or breastfeeding
- Request of the primary care provider if s/he thinks the study is no longer in the best interest of the participant
- Participant judged by the investigator to be at significant risk of failing to comply with the provisions of the protocol as to cause harm to self or seriously interfere with the validity of the study results

All participants who discontinue therapy will be followed up according to their assigned schedule until the end of the study.

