12.3 Other Study Procedures and Evaluations

12.3.1 Early Termination Visit

Participants who meet any one or more of the following criteria will be discontinued from study treatment:

• Pregnancy

• Any clinical adverse event, laboratory abnormality, intercurrent illness, other medical condition or situation occurs such that continued administration of study treatment is not in the best interest of the participant

• Participant request for premature discontinuation of study treatment A participant who is discontinued from study treatment should still remain on study, and continue with follow up visits as described in the schedule of evaluations.

A participant who withdraws consent will not continue to be followed.

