12.3.2 Managing a participant who becomes pregnant during the study

A participant who becomes pregnant while receiving study therapy will be discontinued from study treatment and treated according to National Tuberculosis Program or local guidelines. The participant will continue with scheduled study follow-up, classified as being on a non-study regimen, and will not receive study radiographs. Pregnancy outcome will be recorded on study forms.

A participant who becomes pregnant while in study follow-up (not on study treatment) will continue with scheduled study follow-up and will not receive study radiographs. Pregnancy outcome will be recorded on study forms.

12.3.3 Managing participants who are discontinued from study treatment in the setting of an adverse event or the investigator judges that discontinuation of study treatment is in the participant's best interest

The site investigator may discontinue a participant from treatment in the event of a severe or serious adverse event, or at any time if the investigator thinks discontinuation is in the participant's best interest.

For study purposes, such participants should continue to be followed in the study for outcome determination in accordance with the study MOOP, unless the participant withdraws consent. The participant should be referred to appropriate local sources of care for management of medical problems that cannot reasonably be managed by the study team.

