10.2 Outcome Definitions

10.2.1 Treatment completion and successful treatment

1HP

Completion of therapy is defined as having completed 28 daily doses of treatment within 6 weeks. Treatment success is defined as having taken at least 25 doses of medication confirmed by patient report and pill count, and having rifapentine or isoniazid detected at least once in urine or DBS specimens.

3HP

Completion of therapy is defined as having completed at least 12 weekly doses of treatment within 18 weeks. Treatment success is defined as having taken at least 11 doses of medication confirmed by patient report and pill count, and having rifapentine or isoniazid detected at least once in urine or DBS specimens.

Figure 2 shows the algorithm that will be used to classify patients as having treatment success of failure. This hierarchical approach begins with self-reported adherence, then uses pill count, and finally a composite of test results for isoniazid in urine and rifapentine and des-RPT in DBS.

[figure not shown]

Figure 2 Treatment Success

For the treatment success outcome, note that when loss to follow up precludes being able to demonstrate the requisite number of doses having been taken, the outcome is classified as "unsuccessful." A sensitivity analysis will be conducted among those who complete their last scheduled visit after 23 weeks on study.

10.2.2 Safety: Numbers of participants with at least one occurrence of Grade 2 or higher targeted safety events and/or discontinuation of study medications because of side effects attributed to study medications.

Targeted safety events are hypersensitivity syndrome, rash, peripheral neuropathy, hepatotoxicity, nausea and vomiting, and drug-related fever.

This study will grade toxicity and adverse events according to the *Division of AIDS (DAIDS) Table for Grading Adult and Pediatric Adverse Events, Corrected Version 2.1* (dated July 2017).

https://rsc.niaid.nih.gov/sites/default/files/daidsgradingcorrectedv21.pdf See Appendix V of the study protocol.

For the primary safety outcome as of 24 weeks, those who do not complete their last scheduled visit after 23 weeks on study will be considered as failures (safety events).

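### Protocol 14.4.2 can be read as ending follow-up for participants whom Section 12.3 keeps on study, and the reading a site adopts decides whether they count as safety events

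*Protocol*

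**What the plan says.** Protocol 14.4.2 is titled as discontinuation of the study. It lists the participant's own request to withdraw, "Pregnancy or breastfeeding", a request from the primary care provider, and "Participant judged by the investigator to be at significant risk of failing to comply with the provisions of the protocol". The last ground carries a threshold: the expected non-compliance must be serious enough to harm the participant or to seriously undermine the validity of the results. The subsection sits under 14.4, whose heading is "Criteria for Discontinuation of Study Medications", and it closes with: "All participants who discontinue therapy will be followed up according to their assigned schedule until the end of the study".

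Section 12.3 points the other way.
- 12.3.1: "A participant who is discontinued from study treatment should still remain on study". Only a participant who withdraws consent is said there not to be followed further.
- 12.3.2, on pregnancy during treatment: "The participant will continue with scheduled study follow-up, classified as being on a non-study regimen". Its second paragraph also keeps scheduled follow-up when pregnancy occurs after treatment.
- 12.3.3: participants stopped for an adverse event, or because the investigator thinks it best for them, are followed for outcomes unless they withdraw consent.
- 12.3.6 is a separate exception: a participant is not followed while incarcerated.

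Section 14.3 refers pregnancy during the treatment phase to Section 12.

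On scoring, SAP 10.2.2 says that "those who do not complete their last scheduled visit after 23 weeks on study will be considered as failures (safety events". Protocol 15.8.3 likewise counts losses as safety failures at 24 weeks. Stopping study drug counts towards the safety outcome only when it is because of side effects.

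**The concern.** Two parts of the protocol give different answers to one question: does a participant who becomes pregnant, or whom the investigator expects not to comply, stay in follow-up to week 24? The scoring rules attach a primary outcome to the answer. If follow-up continues and no targeted event occurs, the participant is not a safety failure. If the site closes participation before week 23, the same participant is one, with no toxicity.

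The non-compliance ground deserves particular care. It is a forecast made by staff who know the arm, in a trial where adherence is itself a primary outcome. Neither document plans a sensitivity analysis of losses for safety; the one for losses concerns treatment success. A distortion of the safety comparison would not show unless off-study decisions and their reasons were recorded and reported by arm.

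**Working it through.** **1. Can 14.4.2 be read as medication-only?** The parent heading and the closing sentence support that reading. Three things stop it from settling the matter.
- 14.4.1 already lists pregnancy or breastfeeding and a request to terminate treatment. A medication-only 14.4.2 would repeat these under a different title.
- The first item in 14.4.2, a request to withdraw, reads naturally as leaving the study.
- The closing sentence protects those who discontinue therapy. A woman who finishes 1HP at week 4 and becomes pregnant at week 10 has not discontinued therapy. She is on the 14.4.2 list and outside its closing sentence, and 14.3 covers only the treatment phase, yet 12.3.2 keeps her in follow-up. Pregnancy tests run to week 24 in both arms, so the case is foreseeable.

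**2. What changes in the outcomes?** Take a participant with no targeted event who would attend the final visit.

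| Situation | Follow-up kept | Follow-up ended before week 23 |
|---|---|---|
| Drug stopped before 25 (1HP) or 11 (3HP) doses, not for side effects | Unsuccessful; no safety event | Unsuccessful; safety event |
| Requirements for success already documented | Success; no safety event | Success; safety event |

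Only the safety entry differs. Leaving the study adds a treatment-success failure only if it also ends treatment or prevents the doses from being documented.

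**3. Size per participant.** With 250 per arm, one such removal adds 1/250 = 0.4 percentage points to that arm's safety failure rate.

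**4. Baseline power for safety.** Inputs from Protocol 15.4: risks of 13% and 6%, between-cluster CV k = 0.1, 125 households of m = 2 per arm, two-sided 0.05. The plan states about 80% power.
- Variance term: V = [p1(1−p1) + p2(1−p2)]/m + k²(p1² + p2²) = (0.1131 + 0.0564)/2 + 0.01(0.0169 + 0.0036) = 0.08496.
- Power: Φ(0.07/√(0.08496/125) − 1.96) = Φ(0.725) = 76.6%.

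This is below the stated figure. The same formula gives 80.4% for outcome 1 (80% v 90%, CV 0.15) and 80.7% for the plan's alternative of 12% v 5%. I use 76.6% as the baseline.

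**5. Illustration.** The documents give no removal rate, so each x below is an assumption. If a share x of an arm is removed before week 23, independently of true events, the observed risk becomes p + (1−p)x.

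| Removed, 3HP / 1HP | Observed risks, 3HP v 1HP | Difference (points) | Power |
|---|---|---|---|
| 0 / 0 | 13.0% v 6.0% | 7.0 | 76.6% |
| 1% / 1% | 13.9% v 6.9% | 6.9 | 72.3% |
| 2% / 2% | 14.7% v 7.9% | 6.9 | 68.2% |
| 5% / 5% | 17.4% v 10.7% | 6.7 | 57.4% |
| 2% / 0 | 14.7% v 6.0% | 8.7 | 89.9% |
| 0 / 2% | 13.0% v 7.9% | 5.1 | 46.7% |

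Equal removal shrinks the difference slightly and costs power. Unequal removal moves the difference in either direction. The higher power in the 2% / 0 row reflects bias, not a gain.

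**The case against.** The best defence is that the protocol already resolves this. The parent heading concerns medications, 14.3 sends on-treatment pregnancy to Section 12, 12.3.2 covers pregnancy on and off treatment, and the closing sentence of 14.4.2 promises follow-up. A site that reads all of this would keep everyone. The non-compliance ground also has a threshold of harm or invalidity, so it is not a licence to drop anyone expected to miss doses. The distortion itself comes from counting every loss as a safety event, which applies to losses of any cause. Some participants judged unlikely to comply would miss the week 24 visit anyway and be scored the same.

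Much of this stands. A reader might infer that 14.4.2 removes these participants outright; the text does not plainly do so. Nor is it exact that Section 12.3 expressly keeps the non-compliant: it never names non-compliance, and only the general rule in 12.3.1 reaches it. Pregnancy is an event, not a site's judgement, so the open-label concern attaches to the non-compliance ground.

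What remains is that the medication-only reading leaves 14.4.2 partly redundant and does not cover pregnancy after completed treatment. A site following the title of 14.4.2 would have text to rely on, and the scoring rule would turn that decision into a primary-outcome failure.

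**Conclusion.** The passages conflict and must be reconciled. If 14.4.2 is taken to end participation before week 23, a participant without toxicity becomes a safety event who would not be one under Section 12.3, at 0.4 points per participant in that arm. The total effect cannot be stated, because it depends on how many sites read 14.4.2 that way and how often its grounds arise. The figures for 1%, 2% and 5% removal are illustrations only.

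Two stronger conclusions are tempting and are not supported.
- A reader might infer failure on both primary outcomes. A participant stopped short of 25 or 11 doses is unsuccessful whether or not follow-up continues, and one with documented success stays a success. The added effect is mainly on safety.
- A reader might infer bias towards 1HP, because 3HP treatment lasts three times as long. That requires a removal rate proportional to time on treatment, which the documents do not give. The safety rule covers all time up to the visit after week 23, and follow-up is the same length in both arms. Non-differential removals would mainly dilute the difference.

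**What to change.** Reconcile 14.4.2 with 12.3.1 to 12.3.3. State that the grounds in 14.4.2, other than the participant's withdrawal of consent, do not end study follow-up and that scheduled visits continue to week 24. Cross-reference the incarceration provision in 12.3.6 so that it is a visible exception. Leave the criteria for stopping treatment unchanged; this point concerns follow-up and scoring only. Record the date and reason for every off-study decision and report them by arm.

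The cost is a protocol wording amendment with ethics review, which Section 18.1 requires for modifications, and a memo to sites. No visits are added, because the schedule already contains them. The downside is that sites must keep scheduling some participants who are hard to retain.

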15. STATISTICAL CONSIDERATIONS

15.1 Overview and General Design Issues

While the 3HP regimen is proven safe and effective in HIV-positive and – negative people, 1HP has only been shown to be safe and efficacious in HIV-positive people. An efficacy study in HIV-uninfected individuals would be useful for purposes of replication of the single study demonstrating the non-inferiority of 1HP, but such a trial would be extremely costly and time - consuming. The ACTG BRIEF TB trial took 6 years at a cost of >\$25 million with its sample size of 3000.

It is likely that a non-inferiority efficacy trial in HIV negatives would require a sample size of at least 4500. In the history of TB preventive therapy, a regimen that is efficacious in one population has always been efficacious in others. For 3HP, efficacy was found to be quite similar in HIV+ people and HIV-negative, as well as in children. What can differ, however, is toxicity and tolerability. As shown with the 2-month rifampin and pyrazinamide (2RZ) regimen, safety in people with HIV does not ensure safety in HIV-negative people. Thus, a safety and adherence study is both necessary and preferred.

1HP is now recommended by the WHO as an alternate first-line regimen for treatment of latent TB infection. The USPHS OI Task Force and the CDC have indicated that they will likely add language recommending 1HP for HIV seropositive adults and adolescents in the near future.

15.2 Study Outcomes

15.2.1 Primary Outcomes

(1) Successful completion of TBT with ≥90% adherence documented by self-report, pill count, and pharmacologic monitoring.

Definitions:

For 1HP, successful completion of TPT is defined as having taken at least 25 doses of self-administered daily medication within 8 weeks of enrollment confirmed by patient report and pill count, and having rifapentine or isoniazid detected in urine and DBS specimens.

For 3HP, successful completion of TPT is defined as having taken at least 11 doses of self-administered weekly medication within 16 weeks as confirmed by patient report and pill count and having rifapentine or isoniazid detected in urine and DBS specimens.

(2) Safety of treatment regimens, defined as occurrence of Grade 2 or higher targeted safety events and discontinuation of study medications because of side effects.

Targeted safety events are hypersensitivity syndrome, rash, peripheral neuropathy, hepatotoxicity, nausea and vomiting, and drug-related fever.

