12.1.4 Follow-up visits

At all Visits for both treatment arms:

Targeted Physical Exam

A targeted physical examination at post-entry visits is to include vital signs (temperature, pulse, respiration rate, and blood pressure) and weight. It should be driven by any previously identified or new signs or symptoms including diagnoses that the participant has experienced since the last visit.

Signs and Symptoms

Record all signs and symptoms and grate according to the DAIDS grading criteria.

Diagnoses

Record all new diagnoses or worsening of a pre-existing condition, and grade according to the DAIDS grading criteria.

Concomitant Medications

All new concomitant medications taken since the last report and change in current concomitant medications since the last report should be recorded, including start and stop dates.

Study Treatment Modifications

Record all study drug modifications, including initial doses, participantinitiated and/or protocol-mandated modifications, inadvertent and deliberate interruptions (i.e., 3 or more missed doses) at each visit. Record permanent discontinuation of treatment.

Patient Costing Survey

The patient costing questionnaires will be administered to 50 patients who were selected at the time of enrolment to complete this survey at two time points, namely the completion of treatment and the end of the follow-up period.

Arm A: Rifapentine 600 mg daily and isoniazid 300 mg daily for 4 weeks (1HP)

Arm A will have 250 participants.

Weeks 0-4

All daily doses of rifapentine/isoniazid (HP) will be self-administered at home by the participant, except for the initial dose which will be supervised by the study staff in clinic. Participants will record their HP dose taking and doserelated food intake/time on a medication diary card (Appendix II). The research pharmacy at each site will dispense 15 or 16 rifapentine blister packs, each with 8 tablets (2 doses per pack, 30-32 doses total) and 30 or 32 300 mg INH tablets to cover the visit window period. An extra 2-4 days of medication will be provided to allow for vomited doses and to reduce the likelihood of medication dumping. Participants will be told to bring unused medication back to clinic for the 2 and 4 week visits. At enrolment, 50 participants will be selected to complete a patient costing survey and be asked to complete this survey two additional times during their follow visits (at completion of treatment and at the end of the study participation).

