- urine pregnancy test for participants of childbearing potential

Week 24 (+/- 3 days)

The study team will conduct the following assessments:

- -TB symptom screen
- targeted physical exam
- adverse event assessment
- urine pregnancy test for participants of childbearing potential
- patient costing survey

This is the final study visit
Arm B: Rifapentine 900 mg once-weekly and isoniazid 900 mg once- weekly for 12 weeks (3HP)

Arm B will have 250 participants.

Weeks 0-4

All once-weekly doses of rifapentine/isoniazid (HP) will be self-administered at home by the participant, except for the initial dose which will be supervised by the study staff in clinic. Participants will record their HP dose taking and dose-related food intake/time on a medication diary card (Appendix II).

The research pharmacy at each site will dispense 4 rifapentine blister packs, each with 8 tablets (1.33 doses per pack, 5.33 doses total) and 12 or 15 300 mg INH tablets to cover the visit window period. An extra dose of medication will be provide to allow for vomited doses and to reduce the likelihood of medication dumping. Participants will be told to bring unused medication back to clinic for the 2, 4, 8 and 12 week visits.

At enrolment, 50 participants will be selected to complete the patient costing survey and be asked to complete this same survey two additional times during their follow visits (at completion of treatment and at the end of the study participation)

Week 2 (+/- 3 days)

The study team will conduct the following assessments:

- TB symptom screen
- targeted physical exam
- adverse event assessment
- adherence questionnaire
- Pill count of HP, review of medication diary card
- CBC
- chemistry panel including liver function tests
- Urine pregnancy test for participants of childbearing potential

Week 3 (+/- 3 days for visit) Day 22 (24 hours after HP dose #4 was taken)

The participant will arrive to clinic at least an hour early, so that everything is in place for drug sampling events to begin on time.

Collect the blood and urine for drug sampling and record the exact time the sample blood and urine was collected.

The study team will conduct the following assessments:

- TB symptom screen
- targeted physical exam
- adverse event assessment
- adherence questionnaire

- pill count of returned HP, review of medication diary card

- CBC

- chemistry panel including liver function tests
- Dried blood spot and urine collection for drug sampling

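### Success must be confirmed by pill count and may be reached up to week 8 (1HP) or week 16 (3HP), but the last scheduled counts are at week 4 and week 11/12

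*Protocol*

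**What the plan says.** **Success definition (protocol 15.2.1).** 1HP needs "at least 25 doses of self-administered daily medication within 8 weeks of enrollment confirmed by patient report and pill count". 3HP needs "at least 11 doses of self-administered weekly medication within 16 weeks as confirmed by patient report and pill count". Both also need drug detection.

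**After a suspension (protocol 14.2.7).** The time limits are the same: "participants in Arm A will have 8 weeks from enrollment to complete 28 doses of HP" and "Participants in Arm B will have 16 weeks from enrollment to complete at least 11 doses of HP".

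**When adherence is measured (protocol 12.1.4, Appendix I).**
- Arm A participants are told to "bring unused medication back to clinic for the 2 and 4 week visits". Pill count, diary review and questionnaire are listed at those two visits only. The week 8 visit has a TB symptom screen, examination, adverse event assessment and pregnancy test.
- Arm B participants are told to "bring unused medication back to clinic for the 2, 4, 8 and 12 week visits". The last count is at week 12 in the text but at week 11 in Table 1B. Week 16 has none.

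**Other time limits.** Protocol 12.1.5 and SAP 10.2.1 define completion within 6 weeks (1HP) and 18 weeks (3HP). They put no time limit on treatment success, but still require confirmation by report and pill count. SAP Section 7 says the adherence outcome uses data through 24 weeks.

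**Unconfirmed participants.** Protocol 15.8.3 scores losses to follow-up at week 4 (1HP) or week 12 (3HP) as unsuccessful. SAP 10.2.1 does so when loss prevents the doses from being shown. The text of neither document covers someone still in follow-up who finishes after the last count. The algorithm in Figure 2 was not available for this review.

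**The concern.** The measurement schedule stops before the period in which the outcome may occur. It leaves uncovered 4 of the 8 weeks allowed in 1HP and 4 to 5 of the 16 allowed in 3HP.

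The protocol itself creates late finishers. Sections 14.2.1 to 14.2.3 call for treatment to be held for several events, including some of Grade 2, and Section 14.2.7 then extends the time to finish. Someone who follows those rules, attends the last count on time and takes the remaining doses afterwards meets the dose requirement, but the schedule never collects the evidence the definition asks for.

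This is a primary outcome, and the sample size has almost no reserve above 80% power. True successes recorded as failures would lower the observed rates. If the loss were larger in one arm, the estimated difference would be biased as well.

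**Working it through.** **1. The plan's own power.** Inputs from protocol 15.4: 80% v 90%, households of about 2 (m = 2), CV k = 0.15, 250 per arm (125 households), two-sided 0.05.

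V = [p0(1−p0)/m + p1(1−p1)/m + k²(p0² + p1²)] / (p1−p0)²

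V = [0.080 + 0.045 + 0.0225 × 1.45] / 0.01 = 0.157625 / 0.01 = 15.76

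Households per arm = 1 + (1.96 + 0.8416)² × 15.76 = 124.7, that is 125, or 250 people. Power at 125 households = Φ(√(124/15.76) − 1.96) = 80.1%. The stated figure reproduces.

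**2. What 1HP can show at the last count.** Take dose 1 on Day 0. The week 4 count is made before that day's dose, but 12.1.4 lets a stable participant take it at that visit. Crediting it, a visit on Day v with h missed days gives v + 1 − h doses (28 at most), so 25 is reachable only if h ≤ v − 24.

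| Week 4 visit | Missed days still allowing 25 | 25 cannot be shown after |
|---|---|---|
| Day 25 | 1 | 2 or more |
| Day 28 | 4 | 5 or more |
| Day 31 | 7 | 8 or more |

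If the visit-day dose is not credited, each limit falls by one day. By Day 56 there are 57 daily slots, so up to 57 − 25 = 32 missed days would still allow 25 inside the 8-week limit.

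**3. The same for 3HP.** Weekly slots fall on Days 0, 7, 14 and so on.
- Table 1B, week 11 less up to 3 days (Days 74–76): 11 slots have passed (Days 0–70), so one lost week leaves 10.
- Day 78: 12 slots, so one lost week leaves 11.
- Day 85, the label in 12.1.4: 13 slots, so two lost weeks leave 11.
- Day 112 (week 16): 17 slots, so six lost weeks would still leave 11.

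**4. A one-week hold in each arm.** In 1HP it leaves 26 − 7 = 19 doses on Day 25, 29 − 7 = 22 on Day 28 and 32 − 7 = 25 on Day 31. In 3HP it leaves 10 on Days 74–76, and 11 or more can be reached from Day 78. 1HP looks more exposed to short holds, but both arms have the gap.

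**5. Illustrative effect on power.** The share of true successes left unconfirmed is assumed; the documents give no figure. The formula is that of step 1 with 125 households per arm.

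| Points lost, 1HP / 3HP | Rates compared | Power |
|---|---|---|
| 0 / 0 | 90% v 80% | 80% |
| 1 / 0 | 89% v 80% | 70% |
| 2 / 0 | 88% v 80% | 59% |
| 3 / 0 | 87% v 80% | 48% |
| 2 / 1 | 88% v 79% | 69% |
| 2 / 2 | 88% v 78% | 77% |

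Equal loss costs little; unequal loss costs much.

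**The case against.** A reader might infer that late finishers cannot be confirmed at all, that they count as failures, and that the outcome is therefore biased against 1HP. The documents do not support going that far.

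- **Confirmation is not impossible.** Protocol 11.1.4 plans self-reported dosing at each monitoring visit and lists pill counts without fixing the weeks. Section 12.1.4 records treatment interruptions at all visits. Appendix II asks for the diary at every visit. Under 12.3.9, a visit outside its window is made up with all its procedures. These points stand. They do not close the gap for someone who attends on time and finishes later, because no later count is required and unused medication is not requested.
- **Scoring as a failure is inferred.** It follows from the definition, but the written rules concern losses to follow-up, and Figure 2 could not be consulted.
- **A one-week hold does not always put 1HP out of reach.** On Day 31, with the visit-day dose, 25 is just reachable.
- **The direction is not shown.** 3HP has the same gap, early week 11 visits leave a one-week hold at 10, and the protocol expects more events or discontinuations in 3HP (13% v 6%). A loss confined to 1HP would also work against the superiority claim, not for it.
- **The 6% does not measure the share affected.** It includes people who stop for good, who are not late finishers, and not every Grade 2 targeted event leads to a hold under Section 14.2.

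What remains is a required confirmation with no scheduled occasion in the last part of the permitted period.

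**Conclusion.** The mismatch is real, affects both arms and should be corrected. It remains under each time limit in the documents (8/16 weeks, 6/18 weeks for completion, or none for success), because the last scheduled count precedes all of them. Participants who finish late but within the rules have no scheduled confirmation and would probably be scored unsuccessful.

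The dose limits rest on dose 1 being Day 0 and on crediting the visit-day dose. The number of people affected is unknown, so the power figures only show sensitivity and do not predict a loss. Greater exposure of 1HP to short holds is supported by the schedule arithmetic; a net bias against 1HP is plausible but not demonstrated.

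**What to change.** 1. Reconcile the time limits: 8/16 weeks in protocol 14.2.7 and 15.2.1, against 6/18 weeks for completion and no limit on success in protocol 12.1.5 and SAP 10.2.1. Reconcile also the week 11 and week 12 placing of the last Arm B count. Which limit applies is for the investigators to decide.
2. Add pill count, diary review and adherence questionnaire to the existing week 8 (Arm A) and week 16 (Arm B) visits for anyone not yet confirmed, or to the existing visit at or after the end of the reconciled window. Ask these participants to bring remaining medication. Amend 12.1.4 and Tables 1A and 1B.
3. State in the SAP that the dose count is cumulative to the end of that window. Where the count is made after the window closes, use the diary dates to place the doses.
4. State how a participant still in follow-up but without a final count is classified.

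The cost is a few minutes for a minority of participants at visits that already take place, plus protocol, case report form and SAP wording. No new visit and no larger sample is needed.
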